4. ESTIMATED DURATION OF THE STUDY

5 years

5. LAY LANGUAGE SUMMARY OR SYNOPSIS (no more than one paragraph)

Mood, anxiety, and traumatic stress disorders are common psychiatric conditions - affecting over 40 million U.S. adults - and are leading causes of disability worldwide. People with these conditions are commonly plagued by difficulty controlling distressing personal thoughts and memories, collectively referred to as repetitive negative thinking symptoms. Models suggest that repetitive negative thinking is driven by executive functioning deficits, such that cognitive resources are insufficient to downregulate unwanted thoughts. Executive functioning deficits could be a promising treatment target but are not typically addressed with existing interventions. The long-term goal advanced by this project is to develop effective, mechanistic cognitive training programs that can improve cognition and reduce symptoms associated with mood, anxiety, and traumatic stress disorders. The objectives of this proposal are first to determine the optimal dose of a cognitive training program designed to improve executive functioning in this population using behavioral and neural outcomes. Our central hypothesis is that repeated training exercises will enhance executive functioning and will lead to a reduction of repetitive negative thinking in mood, anxiety, and traumatic stress disorders. The project will randomize participants with depression, anxiety, and/or traumatic stress disorders to one of two doses of cognitive training or a no-treatment control condition. We will examine executive functioning change with cognitive task performance and functional neuroimaging assessments. We will assess the relationship between change in executive functioning and clinical symptoms.

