Targeted interventions for executive functioning represent an unmet therapeutic need. Estimates of non-response following first-line pharmacotherapy ranges from 30-70% and up to half of patients with mood, anxiety, and traumatic stress disorders do not adequately respond to cognitive behavioral therapy. Executive functioning deficits do not consistently remit in individuals with these disorders who complete standard treatments. Most psychosocial and pharmacological treatments are distal to cognitive mechanisms and only indirectly address cognitive skills. There is a continued need for treatment development to improve clinical response and reduce the burden of these disorders, particularly approaches that address executive functioning.

Targeting executive functioning in treatment would likely result in clinical symptom improvement for several reasons. First, work from our team and others suggest that improving executive functioning directly improves thought regulation, resulting in less repetitive negative thinking. Second, improving executive functioning would likely have helpful downstream effects because repetitive negative thinking exacerbates other clinical symptoms (e.g., negative mood, suicidality), including preceding and predicting worsening affective symptoms. Third, improving executive functioning could mitigate certain stressors that are partially rooted in ineffective cognitive functioning and worsen symptoms. This proposal seeks to test an executive functioning training program previously tested in our group in healthy participants and participants with PTSD in a broader transdiagnostic group of individuals.

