COGENT, dose, and randomization: Following the baseline assessments, participants will be randomized to receive COGENT for 4 weeks (n=32) or an assessment-only control condition that receives clinical, cognitive, and MRI assessments at the same time points (n=32), stratified by diagnostic category (primary mood vs. primary anxiety/traumatic stress). In the basic COGENT training program framework, participants will view a series of items to be remembered, following by a secondary processing task where sentence puzzles are

solved. Participants will receive feedback about their accuracy at the conclusion of each set, and an adaptive algorithm will be used to ensure enough difficulty is maintained. The algorithm titrates advancement to the next trial based on meeting at least 85% accuracy on the prior set of trials. Our preliminary data indicate that a session frequency of 8 sessions, delivered twice weekly for 4 weeks (approximately 30 minutes per session) sufficiently improved cognitive performance. Participants assigned to COGENT will be randomized to complete dosing previously established in our work, 8 sessions over 4 weeks or a dosing of 16 sessions over 4 weeks based on literature indicating that training durations of 8 hours may be most effective. Randomization will be generated by [name] and will be securely transmitted to the study coordinator. Task-based adherence data will be collected (number of sessions, frequency). Participants assigned to waitlist will be given the option to complete COGENT after all assessments if they wish.

COVID-19 Considerations: During the COVID-19 crisis, participants may be asked to complete the consenting, screening and screening measures, and cognitive paradigms using HIPAA compliant UCSD Zoom telehealth technology to minimize in-person contact. For in-person tasks, all UCSD and Keck safety procedures will be implemented based on the current Ramp Up phase.

Clinical monitoring: We will administer a brief questionnaire at the treatment mid-point, including the GAD7, PhenX depression, and RNT-10 for purposes of identifying individuals with increased symptoms. Any individual reporting >20% increase in inventories will be referred to the PI for evaluation per the Risk Management plan below.

Table: Assessments by visit	Active groups	Waitlist group

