Screening visit MINI CSSRS MRI safety OSU-TBI RNT-10 Demographics GAD-7 Phenx Depression PhenX DSM RRS PSWQ WHODAS CTQ PANAS ACS ERQ PCL-5 AUDIT/DAST/Phenx Nicotine ISI Suicide Cognitions Treatment credibility	X	x
Midpoint clinical check GAD7 Phenx Depression RNT-10	X	
Baseline visit Cognitive assessments MRI	X	X

Cognitive training	X	
Post visit 1 (same as screening visit)	X	X
Post visit 2 (same as baseline visit)	X	X

STATISTICAL DESIGN AND POWER

Primary outcomes: Change in working memory and repetitive negative thinking. To determine whether COGENT engages the target as hypothesized (i.e., improving Ospan behavioral performance), we will analyze the effect of COGENT versus the control on the Ospan total correct score in a 2 (group: combined COGENT conditions, control) x 2 (time: pre-training, post-training) analysis of variance (ANOVA). Our hypothesis will be supported by a significant training by time interaction effect ($p < .05$; medium-large effect size based on power calculations). To investigate optimal dosing of COGENT training, effect size estimates will be compared by dose (8 vs. 16 sessions) for differences in mean change pre- to post-training. This analytic approach will be repeated for the RNT-10 Repetitive Negative Thinking and other symptom measures.

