10. HUMAN SUBJECTS

The current study will recruit 95 individuals enrolled at UCSD with a diagnosis of mood, anxiety, or traumatic stress disorder from psychiatric and primary care clinics. The study will overrecruit with the goal of randomizing 75 individuals for a final evaluable sample of 65.

Inclusion criteria will include:

- 1) age 21-55
- 2) fluent in English (sufficient to understand and complete assessments in English)
- 3) diagnosis of mood, anxiety, or traumatic stress disorder
- 4) clinically elevated repetitive negative thinking

- 5) outpatient status
- 6) 6-week stability if taking SSRI medications

Exclusion criteria will include:

- 1) past year diagnosis of severe alcohol or moderate or greater substance use disorder
- 2) lifetime history of psychotic or bipolar I disorder
- 3) acute suicidality necessitating immediate clinical intervention
- 4) neurodegenerative or neurodevelopmental disorders
- 5) history of moderate or severe traumatic brain injury or other known neurological condition
- 6) sensory deficits that would preclude completing tasks
- 7) conditions unsafe for completing MRI scanning (e.g., metal in body)
- 8) currently receiving psychosocial treatment
- 9) currently receiving psychiatric pharmacotherapy, except SSRIs

There are no inclusion/exclusion criteria pertaining to gender, ethnic background, or health status aside from MRI safety requirements stated above.

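### Randomisation is stratified by diagnostic category, but the Ospan and RNT-10 analysis omits the stratum and no COGENT effect by diagnosis is planned

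*Combined protocol and SAP*

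**What the plan says.** Section 7 (Background and Significance) presents the trial as taking a program "previously tested in our group in healthy participants and participants with PTSD in a broader transdiagnostic group of individuals". The central hypothesis in section 5 (Lay Language Summary) is that training "will lead to a reduction of repetitive negative thinking in mood, anxiety, and traumatic stress disorders". Section 10 admits anyone with a "diagnosis of mood, anxiety, or traumatic stress disorder", provided that repetitive negative thinking is clinically elevated.

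In section 9, under COGENT, dose, and randomization, "participants will be randomized to receive COGENT for 4 weeks (n=32) or an assessment-only control condition", also with n=32, and allocation is "stratified by diagnostic category (primary mood vs. primary anxiety/traumatic stress".

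Under Statistical Design and Power, Ospan is analysed in a "2 (group: combined COGENT conditions, control) x 2 (time: pre-training, post-training) analysis of variance (ANOVA". The hypothesis counts as supported if the training by time interaction is significant at .05. The same approach is repeated for RNT-10 and the other symptom measures. The fMRI group model has group, condition, time and a random subject effect. The only other planned comparison is 8 against 16 sessions. Diagnostic category does not appear as a covariate, moderator or subgroup in any of these analyses, even descriptively.

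**The concern.** There are two linked gaps.

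First, a factor used to restrict the randomisation is left out of the analysis. If the strata change by different amounts over four weeks, that difference stays in the residual. Stratification, however, has already removed it from the comparison of arms. The standard error is then too large, and the test is conservative and loses power.

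Second, the hypothesis names three disorder groups and the trial's novelty is its diagnostic breadth, but the plan produces one average over everyone. A significant average is compatible with similar benefit in both strata and with benefit in only one. Nothing planned would help a reader tell these apart. The converse also applies: a benefit confined to one stratum may be diluted and missed.

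**Working it through.** **Inputs.** From the documents: 32 per arm, significance at .05, two strata. Assumed, because the documents do not give them: a two-sided test, an even split between strata unless stated, effects in SD units of pre-to-post change, and equal variances. The group by time interaction in a two-time-point ANOVA is the two-sample test on change.

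**The plan's own figure.** The plan cites a medium-large effect without a number or a power, so n=32 cannot be strictly reproduced. The pooled standard error is sqrt(2/32) = 0.25. At 80% power the detectable effect is (1.96 + 0.84) x 0.25 = 0.70 SD, or 0.71 with the t distribution. That fits the plan's description, and the sample size is not in dispute.

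**Leaving the stratum out.** Suppose that the strata differ in mean change by g in both arms. With an even split the residual variance becomes 1 + g²/4, while the true variance of the group difference is unchanged because the arms are balanced on stratum.
- g = 1.0: sqrt(1.25) = 1.118, so the effective critical value is 1.999 x 1.118 = 2.235. Power at 0.7 SD is Φ(2.80 − 2.235) = 71%, against 79% with the stratum in the model. Simulation gives the same two values, and a null rejection rate of about 3% instead of 5%.
- g = 0.5: sqrt(1.0625) = 1.031, critical value 2.061, power Φ(2.80 − 2.061) = 77%.
- g = 0: no gain, and including the stratum costs one degree of freedom in the change model (62 to 61).

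**Benefit in one stratum only.** Let s be that stratum's share of the sample, d the effect in it, and zero the effect in the other. The pooled effect is s x d, and approximate power is Φ(4sd − 1.96).

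| Share s | d = 0.7 | d = 1.0 |
|---|---|---|
| 30% | 13% | 22% |
| 50% | 29% | 52% |
| 70% | 50% | 80% |

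Simulation of the t-test, with the unequal effects left in the error term, gives somewhat lower values. At 30% they are about 12% (d = 0.7) and 20% (d = 1.0). At 50% they are 26% and 46%. At 70% with d = 1.0 the value is 74%. The simulated range is therefore about 12% to 74%.

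**What stratum estimates can show.** With 16 per arm in each stratum and 60 degrees of freedom (t = 2.00):
- Within-stratum half-width: 2.00 x sqrt(2/16) = 0.71 SD.
- Half-width for the difference between strata: 2.00 x sqrt(4/16) = 1.00 SD.
- Pooled half-width, for comparison: about 0.49 SD (normal).
- Difference between strata detectable with 80% power: 2.80 x 0.5 = 1.40 SD, twice the pooled 0.70. Power for a difference of 1.0 SD is about 51%.
- With a 30/70 split (normal approximation): 0.89 and 0.59 SD within strata, and 1.07 SD for the difference.

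**The case against.** The case for the plan is substantial. A pooled test is the direct answer for a population defined by elevated repetitive negative thinking. Section 7 argues that its forms share one higher-order factor, and neither the aims in section 6 nor the hypotheses in section 9 promise an effect in each diagnosis. Stratified randomisation serves balance and does not commit the trial to subgroup analysis. Subgroup estimates here will be imprecise. All of this stands. It argues against a confirmatory subgroup test. It does not argue against putting the stratum in the model or reporting estimates with intervals.

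Three stronger readings are tempting, and the documents do not support them.

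- A reader might infer that a one-stratum benefit would be reported as transdiagnostic. The plan has no reporting rule on diagnostic scope, and that outcome first requires a significant pooled test, which is far from certain in the scenarios above. A true effect of exactly zero in one stratum is itself an illustrative extreme.
- A reader might want transdiagnostic wording to depend on both stratum point estimates favouring COGENT, with the conclusion otherwise naming one stratum. That rule discriminates poorly. In simulation with d = 1.0 in one stratum and zero in the other, both estimates still favour COGENT in about 79% of significant trials at a 50% share, and about 61% at 70%. With d = 0.7 at 50% it is about 88%. Naming a stratum from the sign of so imprecise an estimate is no better.
- A reader might expect the strata to show whether training works outside the PTSD group studied before. They cannot, because traumatic stress and anxiety share a stratum.

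**Conclusion.** The point holds as an omission from the analysis plan, not as a flaw that invalidates the primary test. The stratum belongs in the model. The gain depends on how strongly diagnosis predicts change: none if it does not, and about 8 percentage points of power (71% to 79%) if the strata differ by 1.0 SD. Stratum-specific estimates should be pre-specified because the hypothesis spans several disorder groups and the pooled result says nothing about consistency between them. The 12% to 74% range shows only that a one-stratum benefit could meet the success rule. It rests on assumed effects and shares, with 64 evaluable participants. Even with the change, intervals of about ±0.7 SD within a stratum and ±1.0 SD for the difference will leave most questions of consistency open, and consistency across all three disorder groups cannot be shown.

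**What to change.** In Statistical Design and Power, for Ospan and RNT-10:

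1. Keep the pooled group by time interaction as the primary test, with its alpha unchanged.
2. Add the randomisation stratum and stratum by time to that model.
3. In a supportive model that uses no alpha, add group by time by stratum. Report the COGENT-minus-control difference in change with a 95% interval in each stratum, and the difference between strata with its interval, whatever the p-values.
4. Describe the pooled result as an average effect in a mixed-diagnosis sample, and say what the stratum intervals do and do not exclude. Attach no sign-based or significance-based rule to the wording.
5. State the limits: the expected half-widths, and the merging of anxiety with traumatic stress in one stratum.

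The cost is a few lines of text and one to two degrees of freedom, on data already collected. No added participants or assessments are needed. The drawbacks are wide stratum intervals in the report and a more restrained conclusion.

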Telephone screening: Prior to scheduling a study visit, participants will complete a brief phone screening. This screening will ask specific questions regarding eligibility to reduce participant burden, including questions to assess severity of mood and anxiety symptoms, clear exclusions (e.g., medication and psychotherapy status), and MRI safety. No medical record screening will occur. Participants will complete the Repetitive Negative Thinking Questionnaire-10 (RTQ-10), a psychometrically validated self-report measure that assesses disorder non-specific repetitive negative thinking. Clinically elevated repetitive negative thinking for eligibility purposes is defined as scoring above the cutoff recommended for diverging clinical samples (>32).

Screening Visit and Post Visit 1: Assessment of psychiatric disorders (MINI for DSM-5), past and current suicidality (Columbia Suicide Severity Rating Scale; C-SSRS), medications and treatment history, MRI safety screening, and history of head injury (Ohio State University Traumatic Brain Injury Identification Method Short Form; OSU TBI-ID) will occur during assessment for eligibility. Clinical interview measures will be audio and/or videorecorded for reliability assessment for participants who provide A/V consent.

A comprehensive assessment battery will be used to characterize the sample and measure change from pre to post-training. Participants will complete: a) Demographic Characteristics: PhenX Toolkit Mental Health Research Core Tier 1 assessment. b) Psychopathology symptoms: GAD7 items about anxiety and somatic symptoms. The PhenX Depression measure consists of symptoms from the Quick Inventory of Depressive Symptoms. General psychopathology will be assessed using the PhenX DSM-5 Level 1 Cross-Cutting

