14. POTENTIAL RISKS

Interview and Behavioral Assessments: The principal risks associated with completing the assessments are discomfort with the nature of questions, fatigue, and irritability with the testing procedure. These questions and procedures have been well-tolerated in previous studies with participant with anxiety disorders. All participants will be provided with information about local mental health resources, including information about crisis contacts.

Loss of confidentiality: By participating in this project, there is a very slight risk that sensitive personal information including psychiatric information or drug-use information which the subject has provided could become known outside the research setting. If some of the information collected, e.g. whether the subject had used illegal substances, were to become public, it may place the subject at risk for criminal or civil liability or may be hinder the subject's ability to get a job, affect his/her reputation, or have otherwise unforeseen consequences. In addition, there is some stigma associated with drug use; therefore divulging information regarding illicit drug use could be associated with adverse peer reaction. Subject information obtained during this study will remain confidential and be disclosed only with a subject's written permission.

Risks associated with functional magnetic resonance imaging: According to the FDA, there is currently no evidence that MRI with approved scanners of up to 7 Tesla signal strength are associated with adverse effects. However, there are two major sources of risk. First, the subject may experience discomfort being in the confined and sometimes noisy environment of the scanner. The main risks associated with these procedures are fatigue, boredom, and irritability with the testing procedure. The investigator and research assistants are trained to frequently check the subjects about their willingness and ability to continue with testing. If the subjects express concerns about continuing with testing, the investigator has instructed the research assistants to stop testing, offer a break, or, in case the subject is not willing to continue, to terminate the testing session. Overall, however, previous studies have not resulted in any significant discomfort or anxiety expressed by the participating subjects.

Second, the strong magnetic field and data acquisition pose some risks. These include

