Procedures for ensuring professional intervention: If a participant expresses significant distress or discomfort during any study procedure, the PI will be notified. The PI (a licensed clinical psychologist) will meet with the individual to evaluate clinical status and level of risk. Subjects may be referred for intervention as deemed appropriate based on level of distress or other clinical factors. The PI will also provide appropriate referrals for outside mental health services for all consented participants, even if the participant elects not to complete the assessment. Information reported will be kept in confidence with the exception that disclosure of suicidality, homicidality, or child or elder abuse warrant reporting to appropriate authorities. In cases of clinical emergency (e.g., current risk of suicide), participants will be escorted to the Emergency Department, which is immediately adjacent to the ACTRI.

The PI will bear final responsibility for the oversight of participant safety monitoring during the study. The UCSD IRB will be provided with annual reports on recruitment, data, and adverse effects associated with the study. Any incidences of serious adverse effects will be provided to the IRB in an official report as directed by the program's current guidelines. The PI and research staff will meet weekly to address issues in recruitment, data entry and quality, training plan progress, and any clinical or adverse effects issues as they arise.

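### The midpoint referral trigger, a rise of more than 20%, cannot fire on an inventory already at or above about 83% of its maximum; one added clause closes this small safety gap

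*Combined protocol and SAP*

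**What the plan says.** Section 9, Clinical monitoring, describes a short questionnaire at the treatment midpoint, intended to find participants whose symptoms have risen. The rule for acting on it is "Any individual reporting >20% increase in inventories will be referred to the PI for evaluation per the Risk Management plan below".

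The assessment table in section 9 lists this check as "Midpoint clinical check GAD7 Phenx Depression RNT-10" and, as the table is reproduced, marks it for the active groups only. It is the only symptom measurement scheduled between the screening visit and Post Visit 1. Post Visit 1 repeats the screening battery.

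The Risk Management plan (section 15) gives further routes to the principal investigator, none tied to a score. One is "If a participant expresses significant distress or discomfort during any study procedure, the PI will be notified". Another is "In cases of clinical emergency (e.g., current risk of suicide), participants will be escorted to the Emergency Department". Section 15 also provides for weekly meetings of the investigator and staff and for an independent safety monitor.

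**The concern.** A percentage rise needs room above the starting score, and a bounded scale runs out of room at the top. A rule meant to detect worsening therefore becomes harder to meet as the starting score rises, and at some point impossible.

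The sample makes this more than a curiosity. Entry requires a score above 32 on the repetitive thinking scale (section 9, Telephone screening) and a mood, anxiety or traumatic stress diagnosis (section 10), so high starting scores on at least one of the three inventories are to be expected. What is at stake is that a participant who worsens from an already severe score during training may not be sent for evaluation, while a participant with the same or a smaller rise from a lower score is.

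**Working it through.** The plan gives no ceiling or derived figure for this rule, so there is nothing to reproduce. The check is direct algebra.

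**Inputs**
- Threshold: a rise strictly greater than 20% (section 9, Clinical monitoring).
- Inventories: GAD-7, PhenX depression, RNT-10 (same place). I take the RNT-10 to be the scale used for eligibility.
- Eligible repetitive thinking scores: 33 and above (section 9, Telephone screening).
- Scale maxima: not in the documents. Assumed: GAD-7 21; depression 27; RNT-10 either 50 or 40. Scores are taken as integers.

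**Formula.** With earlier score S and maximum M, referral needs a new score above 1.2 × S. The new score cannot exceed M, so referral is impossible when 1.2 × S ≥ M, that is when S ≥ M/1.2 = 0.833 M. At exactly M/1.2 the largest possible rise is exactly 20%, which does not meet a strict inequality. The fraction is the same for every M. The largest rise that can go unflagged in this zone is M − M/1.2 = M/6.

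| Inventory (assumed maximum) | Last score that can trigger, and new score needed | No-trigger zone | Largest unflagged rise in the zone |
|---|---|---|---|
| GAD-7 (21) | 17 → 21 | 18–21 | 18 → 21: 21/18 = 1.167 |
| Depression (27) | 22 → 27 | 23–27 | 23 → 27: 27/23 = 1.174 |
| RNT-10 (50) | 41 → 50 | 42–50 | 42 → 50: 50/42 = 1.190 |
| RNT-10 (40) | 33 → 40 | 34–40 | 34 → 40: 40/34 = 1.176 |

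**Comparison with lower scores.** GAD-7 10 → 13 is 13/10 = 1.300 and is referred; 18 → 21 is the same 3 points and is not. With an RNT-10 maximum of 50, 33 → 40 is 40/33 = 1.212 and is referred at 7 points; 42 → 50 is 8 points and is not.

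**Other readings of 20%.** If it meant 20% of the scale range, the zone would start at 17 of 21, 22 of 27, 42 of 50 (scale 10–50) or 32 of 40 (scale 0–40). If it meant a rise relative to the score above the scale minimum, it would start at 18, 23, 44 or 34. Across all of these the zone starts between 80% (32/40) and 88% (44/50) of the maximum. The gap does not depend on one reading; its edge does.

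**Search for another score trigger.** Sections 9 and 15 were read for a point change, severity level or item-level rule. There is none. The safety monitor's duties and the stopping rules contain no symptom-score threshold.

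**The case against.** The strongest reply is that this hardly matters. The check looks for change, and a participant already at the maximum cannot show an increase. Acute suicidality is excluded at entry (section 10), and the MINI and C-SSRS are given at screening and repeated at Post Visit 1. Expressed distress, emergencies and weekly staff review are covered in section 15, and everyone receives crisis contacts (section 14). If the midpoint is week 2 and Post Visit 1 follows training directly, the exposure is about 2 of 4 weeks. Most of this stands, and it is why the point is minor. It does not remove the gap: scores just below the maximum can still rise, and none of these safeguards says what to do with a midpoint score.

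It is also fair to say that the rule has broader loose ends. It does not say which earlier score is the comparator, though the repetitive thinking scale is given both by telephone and at the screening visit, nor whether one inventory is enough. The waitlist arm has no midpoint check marked at all. The first two are settled in the fix; the third is a separate question.

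Two stronger readings are tempting. A reader might infer that half or more of the participants are unprotected, since 9 of the 18 eligible RNT-10 values (33–50), or 7 of 8 (33–40), lie in the zone. These are score values, not participants, and no distribution is given. A reader might also infer that such a participant cannot be referred at all. That does not follow: the limit applies to one inventory at a time, and the other two inventories and the non-score routes remain open.

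A broader remedy, adding a fixed point rise for everyone, goes too far. It would loosen referral where the present rule already works, and it has its own ceiling: a rise of k points is impossible from M − k + 1 upward. Replacing the 20% rule with a 3-point rule would lose current referrals at GAD-7 scores 1–9, where 1 or 2 points now suffice.

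**Conclusion.** The point holds in limited form. Read as a relative rise in raw score, the only score-based trigger cannot fire on an inventory whose earlier score is at or above M/1.2, and unflagged worsening there can reach up to one sixth of the maximum. The fraction follows from the rule alone; the score ranges in the table rest on assumed maxima. The number of participants affected is unknown. No efficacy analysis is touched, and nothing in the documents supports calling the trial unsafe. This is a minor safety improvement, optional and of low priority.

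**What to change.** In section 9, Clinical monitoring, keep the 20% threshold and state how it is applied: a relative rise in raw total score, on any one of the three inventories, compared with the screening-visit score. Add one clause: where the screening-visit score is at or above M/1.2, any rise at midpoint, or a midpoint score still at the maximum, also leads to referral to the principal investigator.

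Under the assumed maxima this adds cover at GAD-7 18–21, depression 23–27, and RNT-10 42–50 (or 34–40). Below those scores the 20% threshold is untouched.

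The cost is one or two sentences, a change to the scoring sheet and no new data. The downside is a few extra evaluations, some for participants who were already severe and have changed little or not at all. The clause also creates a step: on the assumed GAD-7, a score of 17 still needs 4 points while 18 needs 1. That is the price of leaving lower scores alone. With one midpoint check per trained participant, total referrals cannot exceed 32 (the COGENT allocation in section 9), or about 38 if half of the 75 to be randomised in section 10 are trained (75/2 = 37.5). That bound is the whole training arm, so it caps the workload but does not estimate it.

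### The midpoint symptom check and its >20% referral trigger are scheduled for the active groups only; extending them to the waitlist would be a cheap improvement

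*Combined protocol and SAP*

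**What the plan says.** Under Clinical monitoring, Section 9 states: "We will administer a brief questionnaire at the treatment mid-point". The instruments are the GAD-7, PhenX depression and RNT-10, and the stated purpose is to find people whose symptoms have increased. The action rule follows: "Any individual reporting >20% increase in inventories will be referred to the PI for evaluation".

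The visit table in the same section lists "Midpoint clinical check GAD7 Phenx Depression RNT-10" with a mark under the active groups and nothing under the waitlist group. The screening, baseline and two post-training rows are marked for both.

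Two pieces of text point towards wider scope. The referral rule is worded for any individual, and the randomisation paragraph says that controls are assessed on the same schedule as the COGENT arm.

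The Statistical Design and Power text gives "Primary outcomes: Change in working memory and repetitive negative thinking", and the RNT-10 is the named measure for the second of these. The planned analysis uses pre- and post-training values only.

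Several safeguards are not limited by arm. Section 14 says "All participants will be provided with information about local mental health resources, including information about crisis contacts". Section 15 has the PI provide outside referrals for all consented participants and adds "Subjects may be referred for intervention as deemed appropriate based on level of distress or other clinical factors". Post visit 1 repeats the screening battery in both arms, including "past and current suicidality (Columbia Suicide Severity Rating Scale; C-SSRS), medications and treatment history".

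**The concern.** The check exists to detect worsening symptoms, and that need does not depend on receiving training. Under Section 10, waitlist participants have a diagnosed mood, anxiety or traumatic stress disorder and clinically elevated repetitive negative thinking. They may not be in psychosocial treatment, and SSRIs are the only psychiatric drugs allowed. They also receive no training during the wait. Yet the one scheduled step that looks for deterioration partway through is tabled for the other arms.

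There is a smaller measurement issue. A primary outcome questionnaire is completed once more in the active arms than on waitlist, and a positive screen there leads to a clinical evaluation that has no scheduled counterpart among controls.

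**Working it through.** There is no figure in the plan to reproduce; the check is a count from the visit table and the surrounding text.

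**Schedule as tabled (Section 9)**

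| Contact | Active groups | Waitlist |
|---|---|---|
| Screening visit (includes RNT-10) | yes | yes |
| Baseline visit (cognitive tests, MRI) | yes | yes |
| Midpoint check (includes RNT-10; >20% rule) | yes | no |
| Post visit 1 (screening battery again) | yes | yes |
| Post visit 2 (baseline battery again) | yes | yes |

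The blank cell is unlikely to be an artefact of text extraction. The cognitive training row, which must be active-only, shows the same pattern, and the other rows carry both marks.

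**Length of the wait.** Training lasts 4 weeks (Section 9). Section 20 pays $10 per week of treatment or waiting, to a maximum of $40: 40 / 10 = 4 weeks. The midpoint is therefore nominally week 4 / 2 = 2. The weekly payment might bring some contact, but none is described.

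**Symptom checks between the baseline visit and Post visit 1.** Active 1, waitlist 0. With the fix, 1 and 1.

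**RNT-10 administrations from the screening visit to Post visit 1.**
- Active: screening + midpoint + Post visit 1 = 3.
- Waitlist: screening + Post visit 1 = 2.
- Counting the telephone-screen questionnaire as well: 4 and 3.
- With the fix: 3 and 3 (or 4 and 4).

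The exact number of days between symptom measures cannot be derived. Neither the gap from screening to baseline nor the day of Post visit 1 is stated.

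**Number of controls affected.** Section 9 gives n = 32. Section 10 aims to randomise 75; at the equal split implied by 32 and 32, that is 75 / 2 = 37.5, about 38. For 32 controls, the time without a scheduled check is 32 × 4 = 128 person-weeks.

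**PI evaluations that the fix would add.** The documents give no rate of worsening, so the rates below are assumptions.
- 10% of 32: 0.10 × 32 = 3.2.
- 30% of 38: 0.30 × 38 = 11.4.
- The range is about 3 to 11 people.
- At a lower assumed rate of 5%, 0.05 × 32 = 1.6 are expected. The chance of at least one among 32 independent participants is 1 − 0.95^32 = 0.81.

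**The case against.** The strongest defence is that the check is deliberate monitoring of people exposed to an experimental procedure. It is placed at the midpoint of treatment, and controls receive no treatment. The wait is short, acute suicidality is excluded, and Section 18 rates the risks as minimal. On the table's reading, the plan breaks no commitment. That stands, and it is why this is an improvement rather than an error. It does not answer the check's own stated purpose, which is to detect increased symptoms.

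It can also be said that the wording on any individual and on a common assessment schedule already covers the waitlist. That reading is possible, though the reference to treatment and the specific table cell favour the narrower one. Either way an edit is needed: if controls were meant to be included, the table is wrong; if not, the gap is real.

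A further objection is that evaluating controls could lead some into outside care before the post-training RNT-10. This is a true cost. It can already happen in the active arms, and the treatment history at Post visit 1 would record it.

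A reader might infer more than the documents support:
- **That controls have no safety provision, or no route to referral.** Crisis information goes to all participants and PI referral is open to all consented participants. Only the scheduled trigger is limited to the active arms.
- **That the RNT-10 comparison is materially biased.** The midpoint value is not an analysed time point, and one extra completion of a questionnaire probably matters little.
- **That adverse events are known only if volunteered.** No general adverse-event question is listed at any visit, but Post visit 1 asks both arms about suicidality, psychiatric diagnoses, medications and treatment. What remains is mainly the lack of a stated prompt for medical events, which is missing detail.

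**Conclusion.** The point holds as a low-cost improvement to the design. Followed as tabled, the plan schedules 1 symptom check with a referral trigger during the 4-week interval in the active arms and 0 on waitlist, for about 32 to 38 symptomatic controls. It also gives the RNT-10 3 times against 2.

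These counts rest on the table being the operative statement of scope, which the text leaves slightly open, and on a nominal 4-week wait. The number of controls who would cross the threshold is unknown; any figure for it is an assumption. The case rests mainly on participant safety and only secondarily on equal measurement.

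**What to change.** In the Section 9 visit table, mark the midpoint clinical check for the waitlist group. In the Clinical monitoring paragraph, state that the week-2 GAD-7, PhenX depression and RNT-10, and the >20% referral rule, apply to all randomised participants. Define the midpoint for controls as week 2 of the wait.

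The cost is one brief questionnaire for about 32 to 38 people, roughly 3 to 11 PI evaluations under the assumed 10% to 30%, and possibly some outside care before Post visit 1. The plan does not say whether someone who starts outside care stays in the evaluable sample of 65, so a sentence on that would help. The change makes the scheduled symptom checks and RNT-10 administrations equal. It does not make all contact equal, because active participants also complete 8 or 16 training sessions.

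As an optional addition, one standard question on adverse events and hospitalisation could be put to both arms at the midpoint and at Post visit 1. That is 2 × 64 = 128 to 2 × 75 = 150 short administrations. It would give the annual adverse-event rates promised to the safety monitor in Section 15 a common basis.
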